9.3 STATISTICAL ANALYSES

9.3.1 Main clinical analyses

The main analyses will be the matched-pair comparison of recruitment and overall compliance rates between blinded and open control designs. Details of additional vitamin D supplement use will be recorded at entry, and retrospectively at the 2-year final visit. Failure to report taking at least 19 doses of allocated IMP or to attend the 2-year final visit are included in the definition of non-compliance, so there will be no missing data for the main analyses.

Change in blood level of 25(OH)D from entry to exit will be analysed in relation to self-reported compliance. The effect of treatment on 25(OH)D level, both overall by allocated treatment and in compliant participants, will also be analysed in relation to the pre-treatment 25(OH)D level.

The principal economic issues in the feasibility study will be the overall additional trial costs in blinded practices, to be weighed against the advantages and disadvantages of placebo control in relation to possible bias in self-reporting of minor conditions and suspected side-effects, treatment compliance, and self-medication with vitamin D by controls. The feasibility of collecting appropriate resource use data will also be assessed, specifically the viability of linking HES data to NHS reference costs using Healthcare Resource Group (HRG) information in order to calculate NHS costs, and using participants' medical records to obtain information on the use of primary care services.

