3.1 STUDY OUTCOME MEASURES

3.1.1 Primary outcomes of the feasibility study

The primary aim of the feasibility study is to establish the procedures required to conduct the main trial: our target is to randomise 1,600 participants aged 65-84 through 20 GP practices.

Primary outcome measures:

- 1. The overall recruitment rate (the proportion of invited participants who are randomised) and comparison of recruitment rate in blinded versus open control studies.
- 2. The overall level of compliance with study medication and comparison of blinded medication versus open label vitamin D compliance (to evaluate whether participants taking open label vitamin D are more or less compliant than those who are unaware of IMP status). A randomized participant is defined as compliant:
- (i) If allocated to vitamin D: they report taking at least 19 (79%) of the 24 monthly doses of allocated IMP, and attend the 2-year follow-up visit.
- (ii) If allocated to no vitamin D (whether placebo or open control): they report taking a total of <300,000 IU of vitamin D supplements over the 2 years of the study, and attend the 2-year follow-up visit. (The current UK RDA of 400 IU/day is 292,000 IU over 2 years).

These will be combined as a single outcome measure, which is the number of people we must invite to get one person complying with allocated treatment, to demonstrate that the main trial is feasible. It equals the number invited divided by the number randomised and compliant.

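### The compliant-participant effect on 25(OH)D drops high supplement users from the controls only, so it is not like-for-like and is expected to overstate the study-dose effect

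*Protocol*

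**What the plan says.** Protocol 9.3.1 analyses the effect of treatment on 25(OH)D "both overall by allocated treatment and in compliant participants", in relation to the pre-treatment level.

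The only full definition of compliance is in 3.1.1, and it has two branches:

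- Allocated to vitamin D: "they report taking at least 19 (79%) of the 24 monthly doses of allocated IMP, and attend the 2-year follow-up visit". Supplements bought by the participant are not limited.
- Allocated to placebo or open control: "they report taking a total of <300,000 IU of vitamin D supplements over the 2 years of the study", and attendance at the 2-year visit. No number of placebo doses is required.

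The control threshold is explained by the remark that "The current UK RDA of 400 IU/day is 292,000 IU over 2 years".

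Section 9.3.1 restates the rule more briefly: "Failure to report taking at least 19 doses of allocated IMP or to attend the 2-year final visit are included in the definition of non-compliance". This wording omits the control intake limit. Because 6.1.1 lists the placebo among the IMPs, it can also be read as asking 19 doses of placebo participants.

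On data, 9.3.1 states: "Details of additional vitamin D supplement use will be recorded at entry, and retrospectively at the 2-year final visit". It makes no distinction by arm.

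**The concern.** Attendance is the only condition common to both branches. Beyond that, the vitamin D arms are filtered on study doses and the controls are filtered on their own vitamin D intake, which directly causes the outcome. A participant who starts a strong supplement after randomisation is removed if allocated to control and kept if allocated to vitamin D. The compliant-only difference then contains the study dose plus part of the supplement intake that randomisation had balanced.

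Adjusting for baseline 25(OH)D does not undo this, because the filter acts on intake after randomisation. The entry exclusion in 4.3 (more than 400 IU/day) limits such use but cannot prevent it later, and 2.1 makes contamination of controls a primary objective.

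There is a second consequence. If contamination differs between placebo and open controls, which the trial sets out to learn, the filter removes different shares in the two designs. The compliant-only effect could then differ by design for that reason alone.

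**Working it through.** **Figures from the protocol**

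- 400 IU/day × 730 days = 292,000 IU, and 19/24 = 79%. Both stated figures reproduce.
- Control threshold: 300,000/730 = 411 IU/day.
- Full regimen: 24 × 100,000 = 2,400,000 IU, or 3,288 IU/day. Nineteen doses: 1,900,000/730 = 2,603 IU/day. The midpoint of 19 to 24 doses is 21.5 doses, or 2,945 IU/day. Call this *d*.

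The protocol gives no expected contamination rate and no 25(OH)D response per IU.

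**Formula without confounding**

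Assume a linear response of *s* nmol/l per IU/day, equal supplement use in both arms, and adherence and attendance unrelated to supplements. Let *c* be the share above the threshold and *x* their intake in excess of everyone else's.

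- Compliant vitamin D mean = base + *s·d* + *s*·(intake of the others + *c·x*)
- Compliant control mean = base + *s*·(intake of the others)
- Difference = *s·d* + *s·c·x*

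The excess relative to the study-dose effect is *c·x/d*. The response *s* cancels.

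**Assumed inputs (not in the protocol)**

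*c* from 2% to 20% in each arm; mean intake of those above the threshold 500 to 1,000 IU/day over 411, so 911 to 1,411 IU/day. Setting everyone else's intake to zero makes the hand value slightly high. The simulation applied the 3.1.1 rules to 600,000 people per scenario, with responses of 10 and 20 nmol/l per 1,000 IU/day, 85% taking at least 19 doses and 92% attending.

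| *c* | Intake of high users (IU/day) | Hand value *c·x*/2,945 | Simulated excess |
|---|---|---|---|
| 2% | 911 | 0.6% | 0.4–0.6% |
| 5% | 1,411 | 2.4% | 2.3% |
| 10% | 911 | 3.1% | 2.8–2.9% |
| 10% | 1,411 | 4.8% | 4.6% |
| 20% | 1,411 | 9.6% | 9.0–9.1% |

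Across all 16 unconfounded scenarios the excess was 0.1 to 5.3 nmol/l, on study-dose effects of about 29 to 59 nmol/l.

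**Is the asymmetry the cause?**

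With *c* = 10%, 1,411 IU/day and the lower response, the study-dose effect was 29.46, the compliant-only estimate 30.80, and the estimate with the supplement limit applied to both arms 29.48. In all 16 scenarios the two-arm limit brought the estimate to within about 0.1 nmol/l of the study-dose effect.

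**Adding confounding** (study-dose effect 44.2)

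- Adherers and supplement users with higher background levels: 46.8 on change (+2.6, 6%) and 48.3 on exit level (+4.1).
- Supplement users or adherers with lower background levels: the excess on change stayed positive but fell as low as +0.2. On exit level the estimate fell below the truth in some runs (43.4 to 43.8).

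**The case against.** **The direction is not fixed by the definition.** A reader might infer that the compliant-only estimate is biased upward by construction. The documents do not support that. If the target is taken literally as at least 19 doses with usual supplements against less than 300,000 IU, there is no mechanical bias. Only confounding remains, and its sign cannot be known from the protocol. Upward is the expected direction when the target is the effect of the study dose. This objection stands.

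**The protocol does not call the compliant result the effect of taking the regimen.** Nor does it rank that result above the by-allocation one. Section 4.4 makes the main analyses intention to treat, and 25(OH)D is a secondary outcome. This also stands and keeps the point small. But 9.3.1 does call the quantity an effect of treatment without saying which effect it is.

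**Supplement use is already listed as a determinant of 25(OH)D** (3.1.2, secondary outcome (v)). Adjusting for it might recover part of the imbalance, but 9.3.1 does not tie that adjustment to the compliant comparison.

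**This is detail for the SAP.** Estimator choice usually is. Here, though, the protocol itself fixes both the subset and its definition.

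**A complier-average effect seems the obvious cure.** A reader might define exposure as at least 19 doses, or at least 300,000 IU in controls. That would be worse: 300,000 IU is one-eighth of the 2,400,000 IU regimen, and 1 to 18 doses would count as none. Suppose an effect of 45 nmol/l, 85% adherence, 10% of controls above the threshold and 15 nmol/l higher. Even with no response to partial dosing, the ratio is 0.85 × 45/(0.85 − 0.10) = 51.0, or +6.0. The compliant-only excess is 0.10 × 15 = +1.5. Over assumed ranges of 5–15% contamination, 15–35 nmol/l excess and an effect of 30–60 nmol/l at 85% adherence, simulation gave about 4–16 nmol/l too high for the binary ratio against 0.7–5.2 for the compliant-only difference.

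**Conclusion.** The point holds as a minor one. The two arms of the compliant comparison are selected by different rules, and the control rule selects on a direct cause of 25(OH)D. Overstatement of the study-dose effect is expected but not certain, at roughly 0.4% to 9% of that effect in the unconfounded scenarios. That range depends on assumed contamination and supplement intake, a linear response and equal supplement use in both arms. Confounding by adherence could enlarge, offset or, on exit level, reverse it.

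A compliant estimate above the by-allocation estimate is not in itself evidence of this bias, since removing non-adherers is meant to raise it. The by-allocation estimate is not touched by the compliance filter.

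The discrepancy over placebo doses is separate and reaches further, because it also affects the primary compliance outcome in blinded practices.

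**What to change.** 1. In 9.3.1, name the baseline-adjusted difference in 2-year 25(OH)D by allocation as the effect estimate.
2. Present the compliant subset as descriptive only, and for that display apply the same limit of less than 300,000 IU of own supplements to both arms. The supplement data are already collected. This removes the mechanical asymmetry, but the subset is still selected after randomisation.
3. If an effect of taking the regimen is wanted, use allocation as the instrument and measure exposure as study doses or total IU taken, not as a binary rule mixing 19 doses with 300,000 IU.
4. Reconcile 3.1.1 with 9.3.1 on whether placebo participants must report 19 doses to count as compliant, and use one definition throughout.

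The cost is a few sentences and a few lines of analysis, with no new data. The downside is a slightly smaller compliant subset or, under item 3, a slightly wider interval and reliance on instrumental-variable assumptions.

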9.3.2 Subgroup analyses

25(OH)D level (pre-treatment, and change after 2 years of treatment) will be analysed in sub-groups of 5-year age group and sex. The change in 25(OH)D level will also be analysed in relation to pre-treatment level, adjusted for the negative bias in this correlation. The overall recruitment rate among all registered patients in each practice will also be analysed in sub-groups of age and sex. (A tabulation by 5-year age group and sex of all registered patients will be obtained from each practice for this purpose.)

All analyses will be repeated in subgroups based on pre-treatment blood 25(OH)D level.

9.3.3 Interim reports

A Data Monitoring Committee will be convened (see section 12.1). Interim safety and recruitment analyses will be conducted annually for this feasibility study. The Trial Management Group will collate and clean data detailing all known serious adverse events to date in trial participants. The trial statistician will then conduct an analysis to compare the incidence of SAEs between intervention and control groups, for review by the DMC. If there is a significant difference (p<0.01) in the incidence of fatal or life threatening adverse events an emergency meeting of the DMC will be convened and the Sponsor and Ethics Committee will be consulted to decide whether the trial should be stopped.

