3.1.2 Secondary outcomes of the feasibility study

- (i) The overall level of attrition (failure to attend the final 2-year visit), and a comparison of attrition between open label and blinded practices.
- (ii) Costs of blinded versus open label study designs.
- (iii) Comparison of incidence of serious adverse events between vitamin D and control in blinded practices.
- (iv) Comparison between vitamin D and control of numbers of infections, GP prescriptions and GP visits (a) in blinded practices, and (b) in open-label practices. This will provide an estimate of the bias in these measures in participants allocated to vitamin D in an open control design.
- (v) Blood 25(OH)D concentration at recruitment and at 2 years in relation to allocated treatment and other potential determinants of vitamin D status (self-reported sun exposure, diet and use of vitamin D supplements).
- (vi) Comparison of change in systolic and diastolic blood pressure from recruitment to 2 years between vitamin D and control groups.
- (vii) Cause-specific mortality and cancer incidence will be ascertained by flagging in the National Health Service Information Centre (NHS IC).
- (viii) Hospital records will be collected by NHS number linkage with the Hospital Episode Statistics (HES) database.

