7.3.1 Recording ARs, SARs, SUSARs and other SAEs

All serious adverse events and all adverse reactions will be detected by three procedures:

- The GP or practice nurse records a serious adverse event or an adverse reaction via the online CRF (VIDAL app) as a result of routine clinical contact with the participant.
- Hospital admissions, cancer diagnoses and deaths will be identified automatically through the Hospital Episodes Statistics (HES) system and the NHS Information Centre.
- 3. Hospital admissions for at least one night will also be independently ascertained from all participants except those allocated to open control through their 3-monthly follow-up replies.

In view of the low-risk nature of vitamin D supplementation, only serious adverse events (whether or not causally related, i.e. SAE, SAR or SUSAR) and suspected non-serious adverse reactions (potentially causally related non-serious event, ie AR) will be recorded

by the GP or practice nurse in the safety section of the online CRF (VIDAL app). The criterion for recording an adverse reaction is that there is a reasonable possibility (ie evidence to suggest) that the IMP caused it. Non-serious adverse events deemed unlikely to have a causal relation to the IMP used in this study should not be recorded on the online CRF. Pre-planned hospitalisations (i.e. planned prior to randomisation) and elective treatments of a pre-existing condition do not need to be reported.

Depending on the nature of the reaction or event, the recording and reporting procedures below should be followed. Any questions concerning the reporting of SAEs and ARs should be directed to the Trial Coordinating Centre in the first instance. A flowchart is given in appendix 2 to aid with safety reporting.

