8. ASSESSMENT AND FOLLOW-UP

All study participants allocated to active treatment or placebo will be contacted at least once a month post-randomisation as outlined below. Those on open control will be contacted only at 24 months. The online CRF (VIDAL app) will send weekly reminders to each GP practice, listing all randomised participants with scheduled or overdue quarterly contact. The Trial Coordinating Centre will monitor adverse events, compliance and change of address online and telephone practices to give appropriate reminders.

Automated phone call, e-mail or text message every month from months 1 to 24:

All participants except those randomised to open control (no treatment) will be reminded to take their study medication every month by automated phone call, e-mail or text message generated by the online VIDAL app. No reply will be required from participants.

E-mail or letter follow up at months 3, 6, 9, 12, 15, 18, 21 and 24:

All participants except those randomised to open control (no treatment) will be contacted quarterly by e-mail or post (participant choice of medium) by the GP practice requesting a short reply by the same medium to record the dates on which the last 3 doses of study medication were taken or report reasons for non-compliance, to report any/no planned change of address, and to report any hospital admissions. The 3-monthly follow-up includes a reminder for participants to contact their GP if they are experiencing ongoing symptoms of hypercalcaemia (persistent nausea, vomiting, thirst, passing excessive amounts of urine or feeling generally unwell). All non-responders will be sent one reminder 3 weeks later and then telephoned by the GP practice staff if they have still not replied. Electronic responses will be recorded onto the VIDAL app by participants via a web-link supplied in the e-mail. Postal responses will be entered by the practice nurse on to the VIDAL app, and reminders will automatically be generated for outstanding items.

GP practice visit at month 24:

A repeat blood sample (9 ml lithium heparin vacutainer), blood pressure measurement, and responses to the same lifestyle questions will be obtained 24 months after randomisation for all 1600 participants to quantify differences in vitamin D status (circulating 25(OH)D level) between the intervention and control groups in the blinded and open-label studies.

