12.1.2 Monitoring procedures

The DMC will review accumulating data in an unblinded fashion in order to monitor safety, efficacy and quality of study conduct.

(a) Safety monitoring

At least annually, the Trial Management Group will collate and clean data detailing all known serious adverse events to date in trial participants, together with an updated HES download of all hospital admissions, and send these data to an independent statistician. The statistician will then conduct an analysis to compare the incidence of SAEs between intervention and control groups for review by the DMC, and the DMC will inform the Trial Management Group whether new findings for the subjects of the trial have changed the benefit / risk ratio of conducting the trial.

(b) Monitoring quality of study conduct

If the DMC observes problems with the study conduct (e.g. with respect to protocol adherence, recruitment or participant withdrawal), it should consider making recommendations to the investigators and the sponsor to improve the quality of the study.

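### The interim SAE comparison for the DMC does not separate the two designs, although open controls lack one SAE source; unless HES linkage is complete, it can lean towards an excess on vitamin D

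*Protocol*

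**What the plan says.** **Interim comparison.** Protocol 9.3.3 asks the statistician to "conduct an analysis to compare the incidence of SAEs between intervention and control groups, for review by the DMC". Section 12.1.2(a) sets the same task, to "compare the incidence of SAEs between intervention and control groups for review by the DMC", and has the DMC say on that basis whether benefit/risk has changed. Both work from every SAE known to date. Neither limits the contrast to blinded practices or splits it by design. Section 12.1.2(a) also supplies an updated HES download of admissions; 9.3.3 does not mention it.

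**How SAEs are found.** Section 7.3.1 lists three routes:
1. entries by the GP or practice nurse;
2. national records: "Hospital admissions, cancer diagnoses and deaths will be identified automatically through the Hospital Episodes Statistics (HES) system and the NHS Information Centre";
3. participants' own reports: admissions of at least one night "will also be independently ascertained from all participants except those allocated to open control through their 3-monthly follow-up replies".

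Section 8 agrees: "All participants except those randomised to open control (no treatment) will be contacted quarterly by e-mail or post", whereas "Those on open control will be contacted only at 24 months".

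**Final analysis.** The secondary outcome in 3.1.2(iii) is "Comparison of incidence of serious adverse events between vitamin D and control in blinded practices". Objective 2.2(ii) likewise limits unbiased adverse-event data to vitamin D v. placebo.

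**Trigger.** In 9.3.3, p<0.01 on fatal or life-threatening events leads to an emergency DMC meeting and consultation with the sponsor and ethics committee.

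**The concern.** The protocol protects its final SAE comparison by confining it to blinded practices, but does not carry that protection into the interim comparison. Read plainly, the interim contrast sets 800 vitamin D participants against 800 controls, of whom 400 are open controls (9.1). Everyone on vitamin D, open-label or blinded, is asked about admissions every three months. Only the placebo half of the controls is asked.

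Practice entries may also be uneven. The quarterly contact reminds participants to see their GP about symptoms of hypercalcaemia, and open controls get no such reminder. Practice staff send that contact, so in open practices they can tell the arms apart.

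The missing self-report route works in one direction, towards more recorded SAEs on vitamin D. At stake is the DMC's reading of benefit/risk during the trial: an artefact could be taken for harm, or a real signal dismissed as an artefact.

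**Working it through.** **The protocol's nearest figure.** Section 9.2 states at least 80% power for a 10-point difference with 400 per arm at two-sided 5%. A two-proportion z-test gives 80.9% for 0.45 v. 0.55, 94.4% for 0.15 v. 0.25 and 99.7% for 0.85 v. 0.95. The statement reproduces. No figure is given for the interim SAE comparison.

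**Inputs**
- From 9.1: 400 per arm, so 800 v. 800 if the designs are combined.
- Assumed, because the protocol gives neither: true SAE proportion *p* (equal in all arms), and *c*, capture in open controls relative to the other three arms.

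**Formulas** (no true effect)
- Recorded on vitamin D: *p*.
- Recorded in pooled controls: (*p* + *cp*)/2 = *p*(1 + *c*)/2.
- Risk ratio: 2/(1 + *c*), whatever *p* is.
- *z* = difference / √[2p̄(1 − p̄)/800], where p̄ is the mean of the two proportions.

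**Results at full 2-year follow-up**

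| *p* | *c* | Vitamin D v. control | Risk ratio | *z* | Chance of two-sided p<0.05 |
|---|---|---|---|---|---|
| 0.20 | 0.9 | 0.200 v. 0.190 | 1.05 | 0.50 | 8% |
| 0.20 | 0.7 | 0.200 v. 0.170 | 1.18 | 1.54 | 34% |
| 0.30 | 0.9 | 0.300 v. 0.285 | 1.05 | 0.66 | 10% |
| 0.30 | 0.7 | 0.300 v. 0.255 | 1.18 | 2.01 | 52% |
| any | 1.0 | equal | 1.00 | 0 | 5% (nominal) |

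**Second set of assumptions.** Take 95% capture in the contacted arms. Open-control capture of 95%, 90%, 80%, 70% and 50% then gives risk ratios of 1.00, 1.03, 1.09, 1.15 and 1.31. With *p* = 0.20, the chance of a false excess on vitamin D at p<0.05 (nominal 2.5%) is 2.5%, 4.4%, 11.8%, 25.7% and 67.4%.

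**An early look.** Reviews are annual and recruitment lasts a year. Assume about 6 months' mean follow-up, so a quarter of the 2-year proportions: 0.20/4 = 0.05 and 0.30/4 = 0.075. With *c* from 0.9 to 0.7, the chance of p<0.05 is about 6-14%. The risk ratio is unchanged.

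**The p<0.01 trigger.** Assume 2-6% with a fatal or life-threatening event and, pessimistically, that deaths are under-captured in open controls as well. With *c* from 0.9 to 0.7, the chance of crossing p<0.01 is 1.1-3.7% (nominal 1.0%). With deaths fully registered it is lower.

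**The case against.** **HES already covers the gap.** The quarterly reply adds only overnight admissions, and HES identifies admissions in every arm. Section 12.1.2(a) delivers a fresh HES download to this very analysis, and deaths and cancers come from national records for everyone. Much of this stands: with complete and current linkage, the bias in admissions and deaths is nil. It is not a full answer. The download is added to the unequal reports and does not replace them. Section 8 says the logistics of linkage are themselves to be assessed in this study. Under 7.1, SAEs also include disability and important medical events without admission, which rest largely on practice entry.

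**Pooling is inferred.** Neither section says that the designs are combined without stratification; the protocol treats them as two studies, and table layout often belongs to a charter or SAP. That is fair, but the protocol itself names one intervention v. control contrast and states the blinded-only restriction for the final analysis alone.

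**Stronger readings.** A reader might infer a large risk of a false alarm at p<0.01. The documents do not support that: the threshold applies only to fatal or life-threatening events, deaths are registered in all arms, and crossing it leads to a meeting and consultation, not automatic stopping. A reader might also apply the 52% above to every look, but it needs the highest assumed SAE rate, the worst assumed capture and full follow-up together. Nor is the final SAE result affected; it is already limited to blinded practices.

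**Conclusion.** The point holds as a possible bias in the overall interim SAE comparison, not a demonstrated one. The unequal source, its direction and the mismatch with 2.2(ii) and 3.1.2(iii) are all in the text. The size is not, because SAE rates, capture rates and HES completeness are not given.

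Under the assumed 20-30% SAE proportion and 70-90% relative capture, the spurious risk ratio is about 1.05-1.18. The false-positive risk is smaller at early looks, and there is no bias if linkage equalises capture. The fatal or life-threatening trigger is much less exposed; only its non-fatal part depends on practice or participant reports.

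**What to change.** Amend 9.3.3 and 12.1.2 before the first DMC look:
- **All-source SAEs:** compare vitamin D v. placebo within blinded practices, in line with 2.2(ii) and 3.1.2(iii).
- **Open practices:** show vitamin D v. open control in a separate table, using only HES and NHS Information Centre events.
- **Both designs together:** combine them, stratified by practice, for linked events only.
- **Trigger:** keep the threshold as it is and all 1,600 participants in the comparison of registered deaths. Compare non-fatal life-threatening events that come from practice or participant reports within blinded practices.

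The whole trigger should not be confined to blinded practices. That would discard half of the equally ascertained deaths with no gain against bias: for an assumed 6% v. 3%, the chance of crossing p<0.01 would fall from about 63% (800 per group) to 30% (400 per group).

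**Cost:** wording and one extra table. The all-source comparison uses 800 participants instead of 1,600, so power at two-sided 5% for 20% v. 25% falls from about 67% to 40%. For a 10-point difference it stays above 80%. Linked deaths and admissions still use everyone.
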